The primary analyses will include all CYP in the ITT sample with complete baseline/outcome data regardless of whether their family is classed as being 'compliant' (i.e. by completing 6+ sessions of MBT-PP). To estimate the impact of the Tavistock programme for CYP from families classed as 'compliant', we will undertake two analyses for the SDQ primary outcome; a per-protocol (or on-treatment) and Compliers Average Causal Effect (CACE) analysis. The on treatment analysis would restrict the Tavistock intervention group to only include CYP from families who received 6+ sessions of MBT-PP and compare SDQ outcomes with the complete CYP sample randomised to receive TAU. To accompany the on-treatment analysis, a descriptive comparison of the compliant, non-compliant CYP / family samples will be presented to examine whether it is reasonable to assume that compliant and non-compliant families are 'similar' (the validity of on-treatment analyses is based on this). If compliant and non-compliant families are systematically different, this provides clear evidence that randomness within the on-treatment analyses has been undermined. The CACE analysis would attempt to address the bias within the on-treatment analysis by adopting an instrumental variable (IV) approach using a two stage Least Squares (2SLS) analysis (Sussman & Hayward. 2010; Tilbrook et al. 2014). The first stage would model the binary compliance measure using the baseline SDQ along with additional variables at the CYP and family levels. This model will be used to generate the predicted compliance for the Tavistock programme. The second stage model will then use the predicted compliance variable in place of the group identifier to generate the CACE estimate for the Tavistock programme. In the event of the on-treatment and CACE estimates being closely aligned, we would favour the reporting of the on-treatment estimate for communicability reasons because it is less abstract / technical compared to CACE. However, if notable differences between the on-treatment and CACE estimates are observed, we would favour the CACE estimate because of this attempts to address the potential bias within on-treatment (i.e. families who comply being different from families that do not comply). STATA IVRegress will be used for this IV approach for estimating CACE.

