Secondary analyses will address the secondary questions of whether, compared to TAU, MBT-PP produces: reduced IPC, lower child perception of IPC, improved parenting style, reduced parent anger expression, improved parent emotional adaptation to the situation, and improved CYP psychological well-being.

Mediation analyses using structural equation modelling will be employed to test whether IPC, lower child perception of IPC, reduced parent anger expression, and improved parent emotional adaptation to the situation are significant mechanisms by which MBT-PP improves CYP adjustment (parent report SDQ scores).

Descriptive statistics will be used to compare the demographics of the sample to the local populations of the LAs. Dropout analyses will be used to assess whether there were systematic differences between participants who were and were not compliant with MBT-PP.

Quantitative data will initially be analysed to establish the extent and nature of any missing data (i.e. MCAR, MCR MNAR). An appropriate imputation solution will be implemented and the ITT analyses will be re-done using this imputed data as sensitivity analyses.

Any parametric test assumptions will then be evaluated and violations to assumptions will be addressed as appropriate (e.g. through data transformations).

Data will be aggregated across the pilot and efficacy studies either pooling the data or using meta-analytic techniques, depending on any design changes that occur from pilot to efficacy, to produce the overall impact estimates of the efficacy study with internal pilot.

All planned statistical analyses will be set out in the Statistical Analysis Plan (SAP) prior to any analysis taking place.

Longitudinal follow-ups

It is possible that the effects of MBT-PP are not seen immediately that the therapy finishes, but take some time to embed into the family system in a way that effects change. We therefore plan to conduct a 3-month follow up. This will take place 3 months from the last session of MBT-PP, or, for those in TAU, 7 months (the length of MBT-PP + 3 months) after the baseline measures. All baseline measures will be repeated.

The analytic procedures employed to analyse the follow up data will be the same as those used to analyse the post-intervention data (but with an additional time point). All analyses will be fully specified in the SAP.

Implementation and process evaluation

Implementation Research Questions (RQs)

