These latter models will be tested in the same way as outlined above for the models with child internalising and externalising behaviours as the final latent variable in the causal chain.

Imbalance at baseline

The characteristics of the MBT and TAU group families and CYP as measured prior to randomisation will be compared. At the CYP level, this will include the T1 mothers SDQ-TD primary outcome and X secondary outcomes, ethnicity, age, gender, EAL and SEND status. At the family level this will include the three minimisation variables (relationship status, CYP ages and parental ethnicity) along with family size and the aggregated primary and secondary outcomes. For scale/continuous variables, means and standard deviations for the MBT and TAU groups will be reported and the difference converted into a Hedges g effect size by dividing the mean difference (MBT – TAU) by the pooled standard deviation. For categorical variables, counts and percentages will be reported.

The analyses of balance at baseline will be replicated for the subsample of CYP included in the final impact analysis for the primary outcome; a complete case subsample. In the case of very low attrition, baseline and complete case analyses should reflect each other. However, as attrition increases, differences are likely to be seen. These analyses will inform the missing data analyses described in the next section.

Missing data

The amount of missing outcome data for the mothers SDQ-TD primary outcome will be summarised, and reasons for missing data discussed in the report, where available. If greater than 5% of CYP have missing mothers SDQ-TD, multi-level logistic regression will be used to model presence or absence of the primary outcome including all available CYP and family-level baseline data as fixed effects, and family as a random effect. Significant variables and possible reasons for the missing data will be discussed in the report.

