A binary variable that distinguishes CYPs with a missing T2 mothers SDQ-TD (= 1) from CYPs with a T2 score (= 0) will be created. Bivariate patterns of missingness will be described (e.g. % missing across all variables included in the ITT analyses plus auxiliary variables at the CYP and family levels) and then modelled using a multilevel logistic regression model with the CYP-level binary missing variable as outcome and the same variables used to examine baseline balance included as explanatory variables at CYP- and family-levels. This represents the ‘drop-out’ model which will provide estimates of the association between the included variables and the probability of being missing from the final impact analysis for the primary outcome.

If none of the covariates included in the ‘drop-out’ model are observed to account for a statistically significant amount of variation in the missing data outcome, imputation will not be feasible. This would lead us to cautiously conclude that the data are missing at random and would discuss the implications of this (which will depend upon the quantity of missing data) in the evaluation report.

If we observe that covariates account for a statistically significant amount of variation in the missing data outcome, we will conduct multiple imputation (MI) analysis to impute the

missing data. The MI analysis will be undertaken using the STATA ‘MI Impute’ command used to impute missing values on the primary outcome (StataCorp, 2023). A ‘burn-in’ of 20 will be used (meaning that the first 20 iterations will be discarded to allow the iterations to converge to the stationary distribution before the imputation) and 100 imputed datasets will be created. The impact analysis for the primary outcome will then be rerun within the imputed datasets using the STATA ‘MI Estimate’ command with Rubin’s rules (Rubin, 1987) used to combine the multiply imputed estimates of the β_1 coefficient in equation 2.0. The coefficient estimates for the original complete case and MI analyses will be compared and discussed in the evaluation report.

Compliance

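### The SAP imputes the primary outcome only if a drop-out covariate is significant, reads non-significance as missing at random, and plans no check on departures from that assumption

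*SAP*

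**What the plan says.** The primary analysis uses complete cases. Protocol, Analysis: "The primary analyses will include all CYP in the ITT sample with complete baseline/outcome data". Protocol, Primary outcome, rules out replacing a missing mother's score with the father's.

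SAP, Missing data, then sets these steps:

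- A threshold: "If greater than 5% of CYP have missing mothers SDQ-TD, multi-level logistic regression will be used" to model missingness.
- The drop-out model has "the same variables used to examine baseline balance included as explanatory variables at CYP- and family-levels". That list, in SAP, Imbalance at baseline, does not name trial arm, and it leaves the number of secondary outcomes as an unfilled X.
- If no covariates "are observed to account for a statistically significant amount of variation in the missing data outcome, imputation will not be feasible". The next sentence reads: "This would lead us to cautiously conclude that the data are missing at random". Only a discussion in the report follows.
- In the opposite case: "covariates account for a statistically significant amount of variation in the missing data outcome, we will conduct multiple imputation (MI) analysis".

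The protocol has two statements on imputation. Its Analysis section is unconditional: "An appropriate imputation solution will be implemented and the ITT analyses will be re-done using this imputed data as sensitivity analyses". Its Assumptions section, under the sample size calculations, plans a missing data analysis followed by multiple imputation if appropriate. Neither sets a significance test as the condition.

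The two sensitivity analyses in SAP, Further analyses, concern the time between T1 and T2 and the trial stage. Neither deals with missing outcomes.

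**The concern.** The rule makes two errors of reasoning.

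First, it draws the wrong conclusion from a null test. If no observed covariate predicts drop-out, the data are compatible with MCAR, but MCAR is not established. The drop-out model cannot tell MAR from MNAR, because the values that would separate them are the missing ones.

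Second, it makes the wrong decision from that conclusion. Standard MI is valid under MAR, so concluding MAR is no reason to leave it out. Feasibility does not depend on predictors of drop-out either; imputation draws on variables related to the outcome.

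When the gate stays shut, the complete-case estimate of the single primary outcome stands with a mistaken statement about the missingness mechanism and no re-analysis. When it opens, MI is run under MAR only. The second gap is the larger one. Mothers report the outcome and evidently know which support they receive: the Participants section of the protocol describes visibly different offers, and no masking is described. Response that depends on how the child is doing, and differs by arm, is the case to examine, and neither branch does so.

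**Working it through.** **1. The plan's own figures.** Inputs from SAP, Sample size calculations: ICC 0.27, R² 0.61 (family) and 0.75 (CYP), n = 1.4 CYP per family, P = 0.50, m = 6. Equation 1.0 is MDES = M × √(1/[P(1−P)]) × √(ICC(1−R²fam)/J + (1−ICC)(1−R²cyp)/(nJ)).

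| Families J | Attrition | M | SE | MDES | SAP states |
|---|---|---|---|---|---|
| 250 | 0% | 2.813 | 0.061 | 0.173 | 0.17 |
| 225 | 10% | 2.814 | 0.065 | 0.182 | 0.18 |
| 200 | 20% | 2.816 | 0.069 | 0.193 | 0.19 |

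The figures reproduce. The SAP states that its attrition figures assume random attrition.

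**2. Power of the gate to flag a real predictor of drop-out.** Assumed: one standardised covariate, two-sided 0.05, 10% missing. Power ≈ Φ(ln(OR) × √(N p(1−p)) − 1.96).

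- N = 350 independent CYP: √(350 × 0.10 × 0.90) = 5.61. OR 1.3: 0.262 × 5.61 = 1.47, power 0.31. OR 1.5: 0.405 × 5.61 = 2.28, power 0.62.
- N = 250 family-level units: √(250 × 0.10 × 0.90) = 4.74. OR 1.3: 1.24, power 0.24. OR 1.5: 1.92, power 0.49.

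One mother reports on all her participating children, so missingness is largely a family event and the second set is closer to this design.

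**3. Chance that the gate opens when nothing predicts drop-out.** For k independent tests at 0.05 this is 1 − 0.95^k: 0.40 for k = 10 and 0.64 for k = 20. The number of tests is an assumption because the SAP leaves it unfilled. Child scores and their family means are also correlated, so independence is only a guide.

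**4. Does the gate separate harmful from harmless missingness?** A simulation used 250 families, the SAP's ICC and R², ten candidate covariates and 400 runs per setting. With drop-out unrelated to outcome, the gate stayed shut in 52% and 61% of runs (base drop-out 10% and 20%), with bias near zero. With drop-out in MBT-PP made to depend on the outcome residual, it stayed shut in 53% and 59%. The complete-case bias was then −0.055 and −0.099 SD over all runs, and −0.057 and −0.100 SD in the runs where it stayed shut. By construction the covariates carried no information about that drop-out. This is the case that the gate cannot see.

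**5. Size of what goes unexamined.** If missing MBT-PP outcomes lie d SD from their MAR prediction, and TAU's do not, bias = (share missing) × d. With d = 0.5 (assumed):

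- 10% missing: 0.10 × 0.5 = 0.05 SD. Two-sided type I error rises from 0.05 to about 0.12 (SE 0.065).
- 20% missing: 0.20 × 0.5 = 0.10 SD. Type I error rises to about 0.30 (SE 0.069).

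Indicative tipping points for an assumed observed effect of 0.20 SD, with the SE held fixed: (0.20 − 0.128)/0.10 ≈ 0.72 SD at 10% missing and (0.20 − 0.135)/0.20 ≈ 0.32 SD at 20%. The values 0.128 and 0.135 are the smallest significant effects with 225 and 200 families.

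**The case against.** The strongest reply is that the gate does little harm to the estimate. Baseline SDQ is already in equation 2.0 at both levels. The complete-case mixed model is therefore valid if missingness depends only on arm, baseline SDQ and the minimisation factors, and MI on those same variables would approximately reproduce it. This stands. The high pilot pre-post correlations (0.78 and 0.87, from 61 CYP in 43 families) do not show that MI would add much; its gain comes mainly from auxiliary variables. It follows that the missing MNAR analysis matters more than the gate. It does not follow that the rule is sound.

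Other replies limit how far the point goes:

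- A reader might infer that the primary result would have no sensitivity analysis at all. The documents do not support that. Time and trial-stage analyses are planned, as are a complete-case balance table and a discussion of reasons for missingness. What is absent is a missing-data re-analysis of the effect.
- A reader might infer that the SAP breaks an unconditional protocol promise. The Analysis section reads that way, but the Assumptions section says imputation is used if appropriate. The SAP is narrower than the former and adds a test found in neither.
- A reader might infer that the gate ignores the mechanism altogether. It does respond to observed predictors: power rises with the odds ratio. It cannot see dependence on the unobserved outcome.
- Arm is not wholly overlooked. The SAP's bivariate description of missingness covers the variables in the ITT model, and Appendix A of the protocol monitors the arm split of losses in the pilot. Vouchers in both arms may limit attrition. None of these measures the effect of informative drop-out on the estimate.

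**Conclusion.** The rule is wrong as written, in both its conclusion (MAR from non-significance) and its action (no imputation). Its practical consequence is that a complete-case primary estimate may be reported without missing-data re-analysis, and that departures from MAR are not tested in any branch. Whether the gate would stay shut in this trial cannot be predicted; with many covariates it may well open by chance.

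The possible size is material. Under an assumed 0.5 SD shift in MBT-PP only, the bias is about 0.05 SD at 10% missing and 0.10 SD at 20%, roughly a quarter to a half of the stated MDES (0.05/0.18 = 0.28; 0.10/0.19 = 0.53). The SAP itself considers both attrition levels, and Appendix A of the protocol treats up to 30% as amber.

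The odds ratios, the number and independence of tests, the 0.05 level for the drop-out tests, the 0.5 SD shift and the 0.20 SD effect are assumptions, not figures from the documents. That mothers know their allocation is an inference. Nothing here shows that the primary estimate is biased, only that the plan would not reveal it if it were.

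**What to change.** In SAP, Missing data:

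1. Delete the significance gate. If more than 5% of CYP lack the T2 mothers' SDQ, always run MI as a sensitivity analysis.
2. Specify the imputation model: trial arm, all equation 2.0 covariates, family clustering, and auxiliary variables where available (for example T3 mothers' SDQ, fathers' SDQ and family size). Fathers' scores will be absent in mother-only families, and T3 may be missing for the same mothers, so state how that is handled.
3. Add a delta-adjusted (tipping-point) analysis, with the shift applied to MBT-PP only and to both arms.
4. Replace the MAR sentence with a statement that there is no evidence against MCAR and that MAR cannot be tested.
5. Put trial arm in the drop-out model, and fill in the number of secondary outcomes in its covariate list.
6. Reconcile the rule with the Analysis and Assumptions sections of the protocol.

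The cost is SAP wording and a modest amount of extra analysis, chiefly the multilevel imputation and the delta runs. No new data are needed and the primary estimate is unchanged. The changes should be made before the outcome data are analysed.
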